### 8.2.1.2 Dose-limiting Toxicity

DLT is defined as the occurrence of any of the following events within the first cycle of treatment (i.e., C1) of entinostat in combination with pembrolizumab that are considered by the Investigator to be at least possibly related to entinostat. A patient that experiences an adverse event meeting DLT criteria in C1 or who receives the full dose of pembrolizumab and all doses of entinostat during C1 without experiencing a DLT is considered a DLT-evaluable patient.

- Grade 4 hematologic and non-hematologic (non-laboratory) toxicities of any duration
- Grade 3 non-hematologic (non-laboratory) toxicity with the exception of Grade 3 nausea, vomiting, and diarrhea that resolve within 3 days following institution of optimal supportive care
- Any Grade 3 or Grade 4 non-hematologic laboratory value if:
  - Medical intervention is required to treat the patient, or
  - The abnormality leads to hospitalization, or
  - The abnormality persists for >1 week.
- Febrile neutropenia Grade 3 or Grade 4:
  - Grade 3 is defined as ANC  $<1.0 \times 10^9/L$  with a single temperature of  $>38.3^{\circ}\text{C}$  ( $101^{\circ}\text{F}$ ) or a sustained temperature of  $\geq 38^{\circ}\text{C}$  ( $100.4^{\circ}\text{F}$ ) for more than 1 hour
  - Grade 4 is defined as ANC  $<1.0 \times 10^9/L$  with a single temperature of  $>38.3^{\circ}\text{C}$  ( $101^{\circ}\text{F}$ ) or a sustained temperature of  $\geq 38^{\circ}\text{C}$  ( $100.4^{\circ}\text{F}$ ) for more than 1 hour, with life-threatening consequences and urgent intervention indicated.

- Grade 4 thrombocytopenia (i.e., platelet count  $<25 \times 10^9/L$ )
- Grade 3 thrombocytopenia with clinically significant bleeding
- Prolonged delay ( $>2$  weeks) in initiating Cycle 2 due to treatment-related toxicity
- Any AE requiring  $>2$  entinostat doses to be held, an entinostat dose reduction, or entinostat discontinuation
- Concurrent elevation of transaminases and bilirubin consistent with Hy's Law criteria

**Note:** The original Hy's Law parameters for treated patients relative to comparator patients have been broadened over time ([Kaplowitz and DeLeve 2003](#), [Zimmerman 1999](#)) to include additional parameters, but still require that these 3 criteria be met:

- i. injury: elevation of  $>3 \times ULN$  ALT or AST activity; and
- ii. function:  $>2 \times ULN$  total bilirubin (another clinical marker for function, such as  $>1.5 \times ULN$  INR may be acceptable if the change is clinically significant in the absence of obstruction) without  $>2 \times ULN$  alkaline phosphatase (ALP); and
- iii. clinical verification to ensure effect is health product-induced and not induced by disease or another cause of injury.

- Grade 5 toxicity

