## **12.2 Populations for Analysis**

The Full Analysis Set (FAS) will serve as the primary population for the analysis of tumor response and other efficacy-related data. The FAS is a subset of all enrolled patients, with patients excluded for the following reasons:

- Failure to receive at least one dose of entinostat and pembrolizumab
- Lack of baseline data for those analyses that require baseline data

A supportive analysis using the Per-Protocol (PP) set may be performed by excluding patients with important deviations from the protocol that may substantially affect the results of the primary efficacy analyses. The final determination on protocol violations, and thereby the composition of the PP set, will be made prior to locking the clinical database and final analysis and will be documented in a separate memo.

The safety population will be used for the analysis of safety data in this study. The safety population will consist of all patients who receive at least one dose of entinostat and pembrolizumab. At least one laboratory or other safety-related assessment subsequent to at least one dose of entinostat and pembrolizumab is required for inclusion in the analysis of a specific safety parameter. To assess change from baseline, a baseline measurement is also required.

A patient that experiences an adverse event meeting DLT criteria during C1 or who receives the full dose of pembrolizumab and all doses of entinostat during C1 without experiencing a DLT, is considered a DLT-evaluable patient.

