#### **12.4.7 Safety Analysis**

Safety will be assessed by clinical review of all relevant parameters including AEs, SAEs, laboratory values, vital signs, and ECG results. Unless specified otherwise, the safety analyses will be conducted for the safety population defined in [Section 12.2](#).

Summary tables and listings will be provided for all reported TEAEs, defined as AEs that start on or after the first administration of study drug. The reported AE term will be assigned a standardized preferred term using the current version of the Medical Dictionary for Regulatory Activities (MedDRA).

TEAEs will be summarized based on the number and percentage of patients experiencing the event by MedDRA (version 18.0) system organ class (SOC) and preferred term. The causal relationship between the occurrence of an AE and study drug will be judged by the Investigator based on the conventions described in [Section 11.3](#). In the event a patient experiences repeat episodes of the same AE, then the event with the highest severity grade and strongest causal relationship to study drug will be used for purposes of incidence tabulations.

Tabular summaries will be provided for:

- DLTs (Dose Escalation/Confirmation Phase only)
- all TEAEs
- TEAEs by relationship to study drug and maximum severity grade
- TEAEs with action of study drug delayed/interrupted or dose reduced
- TEAEs with action of study drug discontinued
- SAEs

For the escalation phase, the observed DLT rate in each dose cohort will be calculated by the crude proportion of patients who experienced DLT with a 2-sided 95% exact binomial CI.

All deaths that occur on study (defined as during treatment or within 90 days of treatment discontinuation) will be reported in a patient listing, which will include the primary cause of death and the number of days between the date of the last dose of study drug and death.

Hematology, serum chemistries, and vital signs will be summarized in a descriptive manner by calculating the mean, standard deviation, median, and range as follows:

- baseline value
- minimum post-baseline value
- maximum post-baseline value
- average post-baseline value

- last post-baseline value

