3.2.4 Safety Analysis Set

Without otherwise specified, the Safety Analysis Set will be used for the analysis of safety data in both the Phase 1b and Phase 2 portions of the study. The Safety Analysis Set will include all patients who received at least one dose of either study drug, entinostat, or pembrolizumab. At least one laboratory or vital sign measurement obtained, subsequent to at least one dose of study treatment, is required for inclusion in the analysis of a safety specific parameter. To assess change from baseline, a baseline measurement is also required.

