Table 14.3.5C	PFS by baseline LDH (%>ULN) (irRECIST) – Phase 2 (FAS)
Table 14.3.5D	PFS by previously treated with ipilimumab and PD-1 (Melanoma cohort only) (irRECIST) – Phase 2 (FAS)
Table 14.3.5E	PFS by Previously treated with BRAF/MEK inhibitor (Melanoma cohort only) (irRECIST) – Phase 2 (FAS)
Table 14.3.5F	PFS by baseline non-classical monocytes (cut-off median for NSCLC, but it might change for other cohorts) (irRECIST) – Phase 2 (FAS)
Table 14.3.5G	PFS by NLR (irRECIST) – Phase 2 (FAS)
Table 14.3.5H	PFS by dNLR (irRECIST) – Phase 2 (FAS)
Table 14.3.5I	PFS by smoking status (current smoker, former smoker, never a smoker) (NSCLC cohorts only) (irRECIST) – Phase 2 (FAS)
Table 14.3.6	Clinical Benefit Rate (irRECIST) – Phase 2 (FAS) (RECIST 1.1) – Phase 2 (FAS)
Table 14.3.7A	PFS status at 6 months (irRECIST) - Phase 2 (FAS)

Table 14.3.7B	PFS status at 6 months – (RECIST 1.1) – Phase 2 (FAS)
Table 14.3.8A	PFS (irRECIST) - Phase 2 (FAS)
Table 14.3.8B	PFS (RECIST 1.1) – Phase 2 (FAS)
Table 14.3.9	Overall Survival – Phase 2 (FAS)
Table 14.3.10	Time to Response – Phase 2 (FAS)
Table 14.3.11	Duration of Response – Phase 2 (FAS)
Table 14.4.1	Overall Treatment-Emergent Adverse Event Information - Phase 2 (Safety)
Table 14.4.1.1	Dose Limiting Toxicities – Phase 1b (Safety)
Table 14.4.1.2	Treatment-Emergent Adverse Events by System Organ Class and Preferred Term -Phase 1b (Safety)
Table 14.4.2	Treatment-Emergent Adverse Events by System Organ Class and Preferred Term - Phase 2 (Safety)
Table 14.4.3	Treatment-Emergent Adverse Events by Preferred Term and Maximum Severity – Phase 2 (Safety)
Table 14.4.4.1	Treatment-Emergent Adverse Events by Preferred Term and Relationship to Any Study Drug – Phase 1b (Safety)
Table 14.4.4.2	Treatment-Emergent Adverse Events by Preferred Term and Relationship to Any Study Drug – Phase 2 (Safety)
Table 14.4.4.3	Treatment-Emergent Adverse Events by Preferred Term and Relationship to Entinostat Alone – Phase 2 (Safety)

Table 14.4.4.4	Treatment-Emergent Adverse Events by Preferred Term and Relationship to Pembrolizumab Alone – Phase 2 (Safety)
Table 14.4.5.1	Treatment-Emergent Adverse Events with Severity of Grade 3 or Greater – Phase 2 (Safety)
Table 14.4.5.2A	Treatment-Emergent Adverse Events with Severity of Grade 3 or Greater and Judged Related to Any Study Drug – Phase 2 (Safety)
Table 14.4.5.2B	Treatment-Emergent Adverse Events with Severity of Grade 3 or Greater and Judged Related to Any Study Drug – Phase 1b

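### The SAP reports the Phase 1b DLT rate on the Safety set, so a dosed patient who leaves Cycle 1 early and is replaced stays in the denominator and can only dilute the rate

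*Protocol*

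**What the plan says.** **Who is evaluable for DLT.** Protocol 8.2.1.2 counts a patient with a DLT in Cycle 1, or one who "receives the full dose of pembrolizumab and all doses of entinostat during C1 without experiencing a DLT is considered a DLT-evaluable patient". Section 12.2 has the same definition among the analysis populations.

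**How the rate is computed.** Protocol 12.4.7 states that "the observed DLT rate in each dose cohort will be calculated by the crude proportion of patients who experienced DLT", with an exact two-sided 95% interval, and names no denominator. The same section sets a default: "Unless specified otherwise, the safety analyses will be conducted for the safety population defined in" section 12.2. SAP 3.10.1 repeats the crude proportion, and SAP 3.10 runs safety analyses on the Safety Analysis Set. SAP 6.1 lists Table 14.4.1.1 as "Dose Limiting Toxicities – Phase 1b (Safety", where the bracketed word is the population label.

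**Who is in the Safety set.** Protocol 12.2: "The safety population will consist of all patients who receive at least one dose of entinostat and pembrolizumab". SAP 3.2.4 is wider; its set "will include all patients who received at least one dose of either study drug, entinostat, or pembrolizumab".

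**What sets the SAP has.** SAP 3.2 defines Full, Per-Protocol, Evaluable, Safety and Pharmacokinetic sets. The Evaluable set turns on the Week 6 assessment and is not a DLT set.

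**Replacement.** Protocol 8.2.1.1 and section 10 allow, but do not require, replacement of a patient who goes off study before the end of Cycle 1 for a cause other than study-drug toxicity.

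**The concern.** The DLT rate should describe patients who were watched through the DLT window or who had a DLT in it. A patient who took the Day 1 doses, had one later assessment and then left for an unrelated reason was not watched through it. The Safety set counts that patient as a non-event. If the patient is replaced, the replacement is counted too, so one planned place contributes two patients to the denominator.

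The error runs in one direction. A leaver who had a DLT is counted under either denominator. The Safety set therefore adds only patients without a DLT: the rate falls if there was any DLT and stays at zero if there was none.

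DLTs and the MTD/RP2D are the Phase 1b primary objective, and Protocol 8.2.1.3 defines the MTD by a DLT rate below 33%. With 3 to 6 patients per dose level, one extra patient can move a printed rate across that limit. The report could then show a rate under 33% at a dose where the rule of two DLTs in up to six had been met, which would puzzle a reader even though the decision was right.

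**Working it through.** **1. The plan's own figures.** Protocol 12.1.1 gives halting probabilities of 3% and 83% at true DLT rates of 5% and 50%. Under the sequential 3+3 rule, a level passes with no DLT in the first three patients, or with one in the first three and none in the next three:

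P(halt) = 1 − [(1−p)³ + 3p(1−p)² × (1−p)³]

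- p = 0.05: 1 − [0.8574 + 0.1354 × 0.8574] = 0.0266, which rounds to 3%.
- p = 0.50: 1 − [0.125 + 0.375 × 0.125] = 0.828, which rounds to 83%.

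Both figures reproduce. They rest on counts of DLTs and do not change with the reporting denominator.

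**2. Following one early leaver.** Assume that the patient takes both drugs on Day 1, has a later safety assessment, leaves before Day 8 for a non-toxicity reason, has no DLT and is replaced.

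| Rule | Leaver counted? | Replacement counted? |
|---|---|---|
| Protocol 12.2 safety population (one dose of both drugs) | Yes | Yes |
| SAP 3.2.4 Safety set (one dose of either drug) | Yes | Yes |
| DLT-evaluable definition (8.2.1.2, 12.2) | No | Yes, if Cycle 1 is fully dosed or a DLT occurs |

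The SAP set would also admit a patient who took entinostat but never received pembrolizumab.

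**3. Effect on the reported rate.** The documents give no DLT or replacement counts, so the numbers of DLTs and leavers below are assumptions. Intervals are exact (Clopper-Pearson): lower limit = Beta quantile 0.025 with parameters (x, n−x+1); upper limit = Beta quantile 0.975 with parameters (x+1, n−x).

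| DLTs | Six evaluable patients | One replaced leaver kept | Two replaced leavers kept |
|---|---|---|---|
| 1 | 1/6 = 16.7% (0.4 to 64.1) | 1/7 = 14.3% (0.4 to 57.9) | 1/8 = 12.5% (0.3 to 52.7) |
| 2 | 2/6 = 33.3% (4.3 to 77.7) | 2/7 = 28.6% (3.7 to 71.0) | 2/8 = 25.0% (3.2 to 65.1) |

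If a dose level with 6 escalation and 9 confirmation patients were tabulated together, two DLTs would give 2/15 = 13.3% (1.7 to 40.5), against 2/16 = 12.5% (1.6 to 38.3) with one leaver kept. That case is uncertain, because SAP 3.1.1 tabulates the dose-determination phase for the 3 mg cohort and moves the 5 mg patients into the expansion tables.

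**4. Using the protocol definition unchanged.** To be evaluable without a DLT, a patient must have had every Cycle 1 entinostat dose. Table 8-3 holds entinostat for Grade 3 neutropenia or uncomplicated Grade 3 thrombocytopenia and resumes the same dose after recovery within a week. Table 8-2 allows discretionary holds at Grade 2 or lower. A patient with such a one-dose hold in Cycle 1 has no DLT on that account and would be left out of the new set because of toxicity. With one DLT and one such patient among six, the rate would be 1/5 = 20.0% (0.5 to 71.6) instead of 1/6 = 16.7%. The new set should therefore keep these patients.

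**The case against.** The strongest reply is that nothing turns on this. Protocol 8.2.1.1 acts on a count, two or more DLTs in up to six patients, and then makes the lower dose the MTD. A printed 2/7 cannot reverse that. Replacement is optional, no leaver is documented, and shifts of about one to five points for one leaver are small beside intervals of roughly 37 to 73 points. It can also be said that the definition's place in Protocol 12.2 shows its purpose as the DLT denominator, so that only the SAP departs from the intent.

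Most of this stands, and it limits the point to reporting. It does not remove it. Protocol 12.4.7 names no denominator other than the safety population, and the SAP label is explicit. If the protocol's intent was the evaluable set, that is a reason to make the SAP match.

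A reader might infer two stronger criticisms that the documents do not support:

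- **That the evaluability definition already removes patients for toxicity.** It feeds no specified analysis, so it removes nobody now. The issue arises only if the definition is adopted unchanged.
- **That the DLT criterion for more than two "entinostat doses to be held, an entinostat dose reduction, or entinostat discontinuation" can never be met, because Cycle 1 has only three doses.** The ordinary reading is that the adverse event must occur in Cycle 1 and that the resulting holds may run later. The neighbouring criterion on a delay of more than two weeks in starting Cycle 2 works the same way. So does a reduction after a hold of two weeks or more, which falls on Cycle 2 Day 1 or later if the hold starts on Day 8. No change of wording is needed.

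**Conclusion.** The point holds as a minor reporting defect in the SAP. Followed as written, the SAP can understate the Phase 1b DLT rate and cannot overstate it relative to the recommended set. For one replaced leaver at a six-patient level the illustrated fall is 2.4 points with one DLT (16.7% to 14.3%) and 4.7 points with two (33.3% to 28.6%, by subtraction of the rounded rates).

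This assumes at least one dosed patient who left Cycle 1 early without a DLT, was replaced and had the later assessment that the safety sets ask for. The documents do not say whether such a patient exists. If none does, the rate is unaffected.

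It should not be inferred that the MTD or RP2D was wrongly chosen. Escalation used counts, and RP2D selection also weighs dose delays, reductions and discontinuations (Protocol 5.1). Phase 1b appears complete: SAP 2.3.1 describes Cohorts 2 and 3 as having entered their second stage, and the protocol starts Phase 2 only after Phase 1b.

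**What to change.** Change the SAP only:

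- **SAP 3.2:** add a DLT-evaluable set following Protocol 12.2, and include patients who missed Cycle 1 doses because of study-drug toxicity, so that nobody is dropped for toxicity.
- **SAP 3.10.1 and Table 14.4.1.1:** use this set as the denominator of the DLT rate, and show the Safety-set rate as a supplement.
- **Study report:** if Phase 1b data had been seen when the denominator was set, say so.

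Dose decisions stand, and the protocol's DLT wording needs no change.

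The cost is one analysis set, one sentence and one table title, with no new data. The rate may look slightly less favourable and its interval slightly wider: for 1/6 the width is 64.1 − 0.4 = 63.7 points, against 57.9 − 0.4 = 57.5 for 1/7.

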#### **8.2.1.3 Maximum Tolerated Dose**

MTD is defined as the highest dose level at which  $<33\%$  of patients experience DLT in C1.

#### **8.2.1.4 Recommended Phase 2 Dose**

The RP2D will be equal to or less than the preliminary MTD. The RP2D will be determined in discussion with the Sponsor, Medical Monitor, and Investigators. Additionally, observations related to immune correlates, and any cumulative toxicity observed after multiple cycles may be included in the rationale supporting the RP2D.

#### **8.2.2 Expansion Phase**

In the Expansion Phase, all patients will receive entinostat PO at the RP2D and schedule on D1, D8, and D15 in combination with pembrolizumab 200 mg via IV infusion over 30 minutes on D1 every 21 days.

### 8.3 Treatment Duration

The maximum duration of treatment for this study is planned to be 35 treatments (approximately 2 years.)

Patients who complete C1 may continue on study as long as, in the Investigator's judgment, the patient is tolerating the study treatment, is not at an increased safety risk, and continues to meet protocol eligibility criteria.

If a patient permanently discontinues 1 of the 2 study drugs (either entinostat or pembrolizumab), the patient may continue to receive monotherapy for up to 2 years, unless alternate therapy is started or another discontinuation criterion is met ([Section 10](#)).

Patients who discontinue both study drugs will receive standard of care outside the auspices of this study at the Investigator's discretion.

After discontinuation of both study drugs, patients will complete an EOT visit within 7 days (+/- 3 days) after the last study drug dose and Safety Follow-up visits 30 days (+/- 3 days) and 90 days (+/- 3 days) thereafter. After completion of the 30-day Safety F/U visit, patients who have not experienced PD are to be followed every 2 months until PD and every 3 months thereafter until death or closure of the study by the Sponsor. The purpose of the post-treatment follow-up is to ascertain the duration of PFS for all patients in the study. After development of PD, surviving patients are to be followed on an every 3-month basis for alternate therapy and survival until closure of the study.

### 8.4 Dose Adjustments

Although entinostat and pembrolizumab have distinct toxicity profiles, they do share some AEs such as fatigue and nausea. There is the theoretical possibility that 1 agent may potentiate the other and hence drug causality will not always be clear. In the event of uncertainty, dose reductions and/or delays will follow the most conservative approach (i.e., delays and/or dose reductions for both drugs) until resolution of the event. No dose reductions will be performed for pembrolizumab. Guidance for delays and or dose reductions for entinostat are presented in [Section 8.4.1](#). Once the entinostat dose is reduced, it cannot be increased. Expected AEs for each agent are summarized in [Section 11.1](#).

## 8.4.1 Entinostat

### 8.4.1.1 Nonhematologic Toxicity at Least Possibly Related to Entinostat

The rules outlined in [Table 8-2](#) are to be followed for the management of non-hematologic toxicities that are definitely or possibly due to entinostat alone, with toxicities graded by the Investigator according to the NCI, CTCAE, Version 4.03.

**Table 8-2 Non-hematologic Toxicity: Dose Modification for Entinostat**

Toxicity	Dose modifications
Grade 4	
Administer symptomatic remedies/ start prophylaxis.
 
Hold dose until recovery to Grade 1 or baseline under the following directions:
 

1. If recovered within 4 weeks of onset (i.e.: <math>\leq 3</math> missed doses), resume study drug as follows:

• If receiving 5 mg, restart study drug at 3 mg

• If receiving 3 mg, restart study drug at 2 mg

• If receiving 2 mg, permanently discontinue study drug

2. If not recovered within 4 weeks (i.e. 4 missed doses), permanently discontinue study drug.

Grade 3	
Administer symptomatic remedies/ start prophylaxis. Hold dose until recovery to Grade 1 or baseline under the following directions:
 

1. If recovered within 1 week, resume study drug at prior dose. If not recovered within 1 week, continue to hold dose.

2. If recovered within 2-4 weeks, resume study drug as follows:

• If receiving 5 mg, restart study drug at 3 mg

• If receiving 3 mg, restart study drug at 2 mg

• If receiving 2 mg, permanently discontinue study drug

3. If not recovered within 4 weeks (i.e. 4 missed doses), permanently discontinue study drug.

Recurrence of the same Grade 3 toxicity despite dose reduction	
If the same <math>\geq</math> Grade 3 event recurs:
 

1. Administer symptomatic remedies/ start prophylaxis. Hold dose until recovery to Grade 1 or baseline.

2. If recovered within 2 weeks, resume study drug as follows:

• If receiving 5 mg, restart study drug at 3 mg

• If receiving 3 mg, restart study drug at 2 mg

• If receiving 2 mg, permanently discontinue study drug

 
If the same <math>\geq</math> Grade 3 event recurs (i.e., third occurrence) despite entinostat dose reduction to 2 mg, as described above, permanently discontinue study drug.

Toxicity	Dose modifications
≤Grade 2	
Administer symptomatic remedies / start prophylaxis.
 
Dosing of study drug may be interrupted at the Investigator's discretion, in consultation with the Medical Monitor.
 

• If dose is held for 4 consecutive weeks, permanently discontinue study drug.

• If toxicity resolves, resume entinostat at the original dose.

If greater than 50% of doses are missed during any 6-week period, discontinue from study drug treatment.

